**e Weight/Height:** Height is required at baseline only. Weight is required at Screening and prior to starting each infusion. The total dose will be calculated based on the weight on the day of the infusion or the most recent weight assuming it was assessed in a reasonable time frame according to Investigator assessment. Study sites should make every effort to measure body weight as close to the infusion day as possible considering the variability of local process from site to site. If the infusion is prepared with the most recent weight assessed in a reasonable time frame, this will not prevent to assess the weight on D1 of each cycle.

- f* For participants with known HIV, hepatitis B and hepatitis C infection under antiviral treatment to confirm controlled infection, and for all participants in Germany and Italy (see details and specific instructions in [Section 10.2](#) and [Section 10.8](#)).
- g* If a tumor biopsy was obtained from a target lesion during eligibility assessment, it is preferred to obtain a new baseline scan.
- h* **CT/MRI:** The initial tumor imaging will be performed within 28 days prior to the C1D1. Scans performed as part of routine clinical management are acceptable for use as the screening scan if they are of diagnostic quality and performed within 28 days prior to the date of enrollment. On study imaging will be performed every 9 weeks (63 ±7 days) after the date of first IMP or more frequently if clinically indicated in the first 45 weeks. Imaging studies should follow calendar days and should not be adjusted for delays in cycle starts or extension. The same imaging technique should be used in a participant throughout the trial. After Week 45 tumor imaging should be performed every 12 weeks (84 ±7 days). CT scan of the **head, neck, chest and abdomen (pelvis is optional)** and any other locations with suspicion or evidence of disease involvement is required for the baseline assessment and during treatment period until PD. After the first documentation of response or the first documentation of progression (if the participant is clinically stable) per RECIST 1.1, confirmatory imaging should be performed no fewer than 28 days later. Alternately, the scan performed at the next scheduled time point (eg, every 63 ±7 days) may be used as confirmation. Tumor assessment is not needed for participants who start another anti-cancer therapy.

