### 3 OBJECTIVES AND ENDPOINTS

**Table 2 - Objectives and endpoints**

| Objectives   | Endpoints  |
|--|--|
| Primary   |  |
| 
 
To determine the antitumor activity of SAR444245 in combination with other anti-cancer therapies in patients with HNSCC
 
                            | 
 
Objective response rate (ORR) defined as proportion of participants who have a confirmed complete response (CR) or partial response (PR) determined by Investigator per Response Evaluation Criteria in Solid Tumors (RECIST) 1.1 (1)
 
  |
| Secondary   |  |
| 
 
To assess the safety profile of SAR444245 when combined with other anti-cancer therapies
 
To assess other indicators of antitumor activity
 
 | 
 
Incidence of TEAEs, SAEs, laboratory abnormalities according to National Cancer Institute Common Terminology Criteria for Adverse Events (NCI CTCAE) V 5.0 and American Society for Transplantation and Cellular Therapy (ASTCT) consensus grading (2)
 
Time to response (TTR) defined as the time from the first administration of investigational medicinal product (IMP) to the first tumor assessment at which the overall response was recorded as PR or CR that is subsequently confirmed and determined by Investigator per RECIST 1.1
 
Duration of Response (DoR), defined as the time from first tumor assessment at which the overall response was recorded as PR or CR that is subsequently confirmed until documented progressive disease (PD) determined by Investigator per RECIST 1.1 or death from any cause, whichever occurs first
 
Clinical benefit rate (CBR) including confirmed CR or PR at any time or stable disease (SD) of at least 6 months (determined by investigator per RECIST 1.1)
 
Progression free survival (PFS), defined as the time from the date of first IMP administration to the date of first documented disease progression determined by Investigator as per RECIST 1.1, or death due to any cause, whichever occurs first
 
 |
| 
 
To assess the concentrations of SAR444245
 
To assess the immunogenicity of SAR444245
 
   | 
 
Plasma concentrations of SAR444245
 
Incidence of anti-drug antibodies (ADAs) against SAR444245
 
   |

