#### Type of participant and disease characteristics

- I 02. Histologically or cytologically confirmed diagnosis of R/M HNSCC that is considered not amenable to further therapy with curative intent. The eligible primary tumor locations are oropharynx, oral cavity, hypopharynx, and larynx (nasopharynx is excluded).

- I 03. Measurable disease

At least 1 measurable lesion (not biopsied at baseline) per RECIST 1.1 criteria. Target lesion(s) may be located in a previously irradiated field if there is documented radiographic disease progression of such lesion(s).

- I 04. Known HPV p16 status for oropharyngeal cancer.

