### 9.2 SAMPLE SIZE DETERMINATION

Overall, in the core phase, the plan is to treat approximately 40 participants per cohort.

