- **Target lesions:** All measurable lesions up to a maximum of 2 lesions per organ and 5 lesions in total, representative of all involved organs, should be identified as target lesions and recorded and measured at baseline. Target lesions should be selected on the basis of their size (lesions with the longest diameter), be representative of all involved organs, but in addition should be those that lend themselves to reproducible repeated measurements. It may be the case that, on occasion, the largest lesion does not lend itself to reproducible measurement in which circumstance the next largest lesion which can be measured reproducibly should be selected. A sum of the diameters (longest for non-nodal lesions, short axis for nodal lesions) for all target lesions will be calculated and reported as the baseline sum diameters. If lymph nodes are to be included in the sum, then only the short axis is added into the sum. The baseline sum diameters will be used as reference to further characterize any objective tumor regression in the measurable dimension of the disease.

- **Non-target lesions:** All other lesions (or sites of disease) including any measurable lesions over and above the 5 target lesions should be identified as non-target lesions and should also be recorded at baseline. Measurements of these lesions are not required, but the presence, absence, or in rare cases unequivocal progression of each should be noted throughout follow-up.

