## Response Criteria

### Evaluation of Target Lesions

- **Complete Response (CR):** Disappearance of all target lesions. Any pathological lymph nodes (whether target or non-target) must have reduction in short axis to <10 mm (<1 cm).

- **Partial Response (PR):** At least a 30% decrease in the sum of the diameters of target lesions, taking as reference the baseline sum diameters.
- **Progressive Disease (PD):** At least a 20% increase in the sum of the diameters of target lesions, taking as reference the smallest sum on study (this includes the baseline sum if that is the smallest on study). In addition to the relative increase of 20%, the sum must also demonstrate an absolute increase of at least 5 mm (0.5 cm). (Note: the appearance of one or more new lesions is also considered progressions).
- **Stable Disease (SD):** Neither sufficient shrinkage to qualify for PR nor sufficient increase to qualify for PD, taking as reference the smallest sum diameters while on study.

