#### Type of participant and disease characteristics

- I 01. PD-L1 expression CPS as determined preferably using a locally approved assay (with an absolute value provided to Sponsor) at local laboratory (for details on PD-L1 assay, please refer to lab manual)
- PD-L1 expression CPS  $\geq 1$  (with an absolute value provided to Sponsor).
- I 02. Provision of tumor tissue:
- **Mandatory baseline biopsy in Core Phase** (minimum 5 slides with 4-5 micron thickness for the first 20 participants who have signed ICF, excluding screening failure participants, minimum 10 slides with 4-5 micron thickness for subsequent participants). Archival tumor tissue samples should be obtained from biopsies done within 6 months, and there should be no systemic anti-cancer therapy between collection of biopsy and enrollment. Slides specifications are detailed in Lab Manual.
  - The Sponsor may approve the written request to enroll, on a case-by-case basis, participants with:
    - location of the tumor not amenable to biopsy due to significant risk, OR
    - less than required number of slides or archival tumor tissue sample collected more than 6 months prior to enrollment.
- I 03. Prior anticancer therapy
- Have not received prior systemic therapy for **R/M disease**. Participants who received systemic therapy as part of multimodal treatment for locally advanced disease are eligible if the systemic therapy was completed at least 6 months prior to enrollment.

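### A target lesion biopsied after the baseline scan may keep its pre-biopsy diameter, so a change caused by the biopsy can enter the measurement that defines the primary ORR

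*Protocol*

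**What the plan says.** - **Biopsied target lesions.** Master protocol 1.3, footnote g, and the same footnote in Substudy 01: "If a tumor biopsy was obtained from a target lesion during eligibility assessment, it is preferred to obtain a new baseline scan".
- **Eligibility.** Master protocol 5.1, I 03: "At least 1 measurable lesion (not biopsied at baseline) per RECIST 1.1 criteria".
- **Tissue.** Substudy 01, 5.1, I 02: "Mandatory baseline biopsy in Core Phase". Archival tissue from the previous 6 months is accepted, and the sponsor may approve exceptions case by case.
- **Baseline imaging.** Master protocol 1.3, footnote h: "The initial tumor imaging will be performed within 28 days prior to the C1D1".
- **Target selection.** Appendix 9 (Selection of Lesions) sets the rule for choosing targets: "All measurable lesions up to a maximum of 2 lesions per organ and 5 lesions in total, representative of all involved organs, should be identified". Size and reproducibility of measurement guide the choice. Biopsy is not mentioned.
- **Partial response.** Appendix 9, Response Criteria: "At least a 30% decrease in the sum of the diameters of target lesions, taking as reference the baseline sum diameters".
- **Primary endpoint.** Table 2: "Objective response rate (ORR) defined as proportion of participants who have a confirmed complete response (CR) or partial response (PR) determined by Investigator". The criteria used are RECIST 1.1.

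**The concern.** I 03 recognises that a biopsied lesion is a poor basis for measuring response, but it protects only one lesion per participant. Footnote g foresees that another target lesion may be biopsied during eligibility assessment and leaves the re-scan to preference. A site can follow every rule and still use a pre-biopsy diameter as the reference for all later scans.

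The order scan, biopsy, first dose is possible because imaging may be up to 28 days old at first dose. Confirmation at least 4 weeks later does not help, since it compares with the same baseline sum and lost tissue stays lost. The cohorts are uncontrolled and judged against historical response rates (master protocol 4.2), so no concurrent arm shares the error. Central reading is optional and retrospective; it would re-read the same baseline image. An analysis rule written later cannot supply a scan that was never taken.

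**Working it through.** **The plan's own figures.** Exact 90% Clopper-Pearson limits at n=40 reproduce all 11 rows of Table 5 to 0.1 point, for example 8/40 = 20.0% (10.4%, 33.2%).

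**Inputs.** The PR threshold is a 30% fall from the baseline sum (Appendix 9). For cohort size, section 9.2 states: "Overall, in the core phase, the plan is to treat approximately 40 participants per cohort". The documents give no lesion sizes, biopsy type or number of biopsies after the scan, so the sizes below are assumptions: one unbiopsied lesion, as I 03 requires, plus one biopsied lesion.

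**Formulas.** Let S be the pre-biopsy baseline sum and d the diameter lost to the biopsy.
- Apparent shrinkage with no drug effect = d / S.
- Further shrinkage of the remaining sum needed for PR = 1 − 0.70·S / (S − d).

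| Assumed lesions, mm (unbiopsied + biopsied) | S | d | Apparent shrinkage | Further shrinkage needed |
|---|---|---|---|---|
| any | any | 0 | 0% | 30% |
| 20 + 10 | 30 | 2 | 6.7% | 25.0% |
| 20 + 10 | 30 | 5 | 16.7% | 16.0% |
| 20 + 20 | 40 | 2 | 5.0% | 26.3% |
| 20 + 20 | 40 | 5 | 12.5% | 20.0% |
| 30 + 15 | 45 | 2 | 4.4% | 26.7% |
| 30 + 15 | 45 | 5 | 11.1% | 21.3% |
| 60 + 15 | 75 | 2 | 2.7% | 28.1% |
| 60 + 15 | 75 | 5 | 6.7% | 25.0% |

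Worked row: S = 30, d = 5. Apparent shrinkage is 5/30 = 16.7%. PR needs a sum of 0.70 × 30 = 21 mm. Going from 25 to 21 mm is 4/25 = 16%.

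**Opposite direction.** If the biopsied lesion were 2 mm larger at the follow-up scan, the 30 mm sum would become 32 mm, and reaching 21 mm would need 11/32 = 34.4%. Swelling therefore works against response.

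**Confirmation.** The confirmatory scan is also divided by S, so d/S is present at both assessments and cancels at neither.

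**Effect on ORR.** One misclassified participant is 1/40 = 2.5 points. For example, 8/40 = 20.0% (10.4%, 33.2%) becomes 9/40 = 22.5% (12.3%, 36.0%).

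**The case against.** The strongest reply is that the exposed group is narrow and the likely loss small.

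- **Excision.** A reader might infer that biopsy alone can create responders: removing a 15 mm node is a 30% fall for any sum up to 15/0.30 = 50 mm, and a 10 mm lesion for any sum up to 10/0.30 = 33 mm. The documents do not support this as the main case. E 06 excludes major surgery or a local intervention in the 28 days before first dose, which is also the imaging window, so excision after the scan is arguably ruled out. The term is undefined, but it cannot cover every biopsy, since footnote g expects one during eligibility assessment.
- **Amount of tissue.** I 02 asks for at least 5 or 10 slides of 4–5 microns; ten at 5 microns come to 0.05 mm of section. Nothing calls for a large specimen, and many biopsies may leave the diameter unchanged.
- **Frequency.** A reader might infer that fresh biopsies are common and usually taken from the largest lesion. Neither is stated. Archival tissue is accepted, and a biopsy before the scan does no harm.
- **Selection.** Appendix 9 favours reproducibly measurable lesions, so an investigator may pass over an altered one. That permits the right choice without requiring it.
- **Unseen material.** The biomarker flowcharts, section 8.6 and the laboratory manual are not visible and may contain advice on which lesion to biopsy.

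These points limit size and frequency. They leave the gap in place: no visible text requires the re-scan or removes the lesion from the target sum.

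**Conclusion.** The point holds as a minor to moderate weakness in how the primary endpoint is measured. The text allows a pre-biopsy diameter to serve as the response reference for a biopsied target lesion, in participants with two or more measurable lesions.

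Under the assumed sizes, a loss of 2 to 5 mm gives 2.7% to 16.7% apparent shrinkage. None of these partial losses reaches 30% alone, but each lowers what treatment must achieve; the largest cuts it from 30% to 16%. No change in diameter means no effect, and swelling acts the other way.

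A reader might conclude that the reported ORR will be inflated. That does not follow: the net direction is not established for small biopsies, and the number taken after the baseline scan is unknown. What can be said is that each misclassified participant moves a 40-participant ORR by 2.5 points. The study makes no formal test (section 9.1), so no error rate or sample size is affected.

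**What to change.** Amend two places together. In footnote g (master protocol, Substudy 01 and any other substudy that repeats it), state that a lesion biopsied after the baseline scan is recorded as non-target unless a new baseline scan is obtained after the biopsy and before first dose. Add the same exception to the target-lesion rule in Appendix 9, which otherwise still tells sites to include all measurable lesions up to the stated limits. Add an eCRF check of biopsy date against baseline scan date.

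The cost is a short amendment and one data check. No extra scan is imposed, because the site may choose the non-target route, and I 03 already guarantees another measurable lesion, so nobody loses eligibility. The lesion is still followed for complete response and progression as non-target. The downside is occasionally one fewer target lesion, which makes the sum slightly less representative. Where a site re-scans instead, transient swelling could enter the new baseline, so the biopsy-to-scan interval should be recorded.

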#### 1.4 BIOMARKER FLOWCHART

## 1.5 PHARMACOKINETIC FLOWCHART

The sampling time-points for pharmacokinetic (PK) and ADA for/against SAR444245 and/or other IMPs may be updated during the course of the study based on the updated knowledge of drug behavior upon notification from the Sponsor.

**1.5.1 All cohorts**

| Cycle                                | Treatment Cycle 1 |                  |          |          | Treatment Cycles 2, 3, 4, 6, 8, 10 + every 4 th cycle thereafter |                  | EOT visit
30 (±7) days after last IMP admin |
|--------------------------------------|-------------------|------------------|----------|----------|---|------------------|--|
|                                      | D1                |                  | D2       | D8       | D1  |                  |  |
| Time after start of SAR444245 dosing | SOI               | EOI              | Any time | Any time | SOI   | EOI              |  |
| SAR444245 PK sample                  |                   | P00 b | P01      |          |   | P00 b |  |
| SAR444245 ADA sample                 | AB00 a |                  |          | AB01     | AB00 a   |                  | ABF00  |

a Samples collected strictly before start of infusion (SOI).

b EOI samples must be taken at end of infusion (EOI) precisely ±5 minutes.

Abbreviations: ADA: anti-drug antibodies; D: day; EOI: end of infusion; EOT: end of treatment; PK: pharmacokinetic; SOI: start of infusion.

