#### Study intervention(s)

##### *Investigational medicinal product*

##### **SAR444245**

- **Formulation:** SAR444245 is provided as a 2 mg/mL concentrate for solution for infusion in a single-dose vial with an extractable volume of 1 mL.
- **Route of administration:** intravenous (IV) infusion.
- **Dose regimen:** 24  $\mu$ g/kg administered as an IV infusion over 30 mins every 3 weeks on Day 1 of each cycle (21 days per cycle) for **up to 35 cycles or until PD.**

Study sites should make every effort to target infusion timing to be as close to 30 minutes as possible. However, given the variability of infusion pumps from site to site, a window of -5 minutes and +10 minutes is permitted.

See substudy protocols for other IMPs.

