Furthermore, the site-specific pegylation extends the plasma  $t_{1/2}$  of IL-2 in SAR444245 in mice and NHP to 9-13 h versus 85 min for aldesleukin in patients.

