## 8.4 PHARMACOKINETICS

[figure not shown]
The sampling time-points for PK and ADA for/against SAR444245 and/or other IMPs may be updated during the course of the study based on the updated knowledge of drug behavior upon notification from the Sponsor.

Instructions for the collection and handling of biological samples will be provided by the Sponsor in the laboratory manual. The actual date and time (24-hour clock time) of each sample will be recorded while for samples to be collected at time of biomarker sampling, no specific time on the given day is necessary.

[figure not shown]
Instructions on the collection, processing, storage, and shipment of samples will be provided in the laboratory manual. Sample analysis will be performed at a laboratory designated by the Sponsor.

Samples collected for analyses of SAR444245 concentration may also be used to evaluate safety or efficacy aspects related to concerns arising during or after the study and any remaining plasma/serum volume may also be used for further exploratory analysis if deemed relevant.

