#### **9.4.3.7 Other secondary endpoints**

Immunogenicity analyses will be described in the SAP finalized before database lock. The PK analysis and pharmacodynamic analyses will be presented separately from the main clinical study report (CSR).

[figure not shown]
Plasma concentrations of SAR444245 will be summarized with descriptive statistics by each cohort.

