**Table 3 - SAR444245 Infusion-related reaction dose modification and treatment guidelines**

| NCI CTCAE Grade   | Treatment   |
|---|---|
| Grade 1
Mild transient reaction; infusion interruption not indicated; intervention not indicated  | If IRR happens during infusion, continuation of SAR444245 a infusion is per Investigator's judgment following close direct monitoring of the participant's clinical status.
SAR444245 infusion may be interrupted at any time if deemed necessary.
If interrupted, IRR will be classified as Grade 2 as per NCI-CTCAE definition.
If IRR happens after completion of infusion, increase monitoring of vital signs as medically indicated until the participant is deemed medically stable in the opinion of the investigator.   |
| Grade 2
Therapy or infusion interruption indicated but responds promptly to symptomatic treatment (eg, antihistamines, NSAIDs, narcotics, IV fluids); prophylactic medications indicated for ≤24 hrs. | Interrupt SAR444245 infusion.
If symptoms resolve within 1 hour of interrupting drug infusion, the infusion may be restarted at 50% of the original infusion rate. Otherwise dosing will be held until symptoms resolve and the participant will be premedicated for the next scheduled dose according to Section 6.1.2.1 of the master protocol.
Give the next infusion at half the infusion rate.
During or after completion of infusion, additional appropriate medical therapy may include but not limited to IV fluids, antihistamines, NSAIDs, acetaminophen, narcotics.
Increase monitoring of vital signs will be as medically indicated until the participant recovers. |

| NCI CTCAE Grade   | Treatment  |
|---|--|
| 
Grade 3
Prolonged (ie, not rapidly responsive to symptomatic medication and/or brief interruption of infusion); recurrence of symptoms following initial improvement; hospitalization indicated for other clinical sequelae
 | 
Permanently discontinue SAR444245. The participant can continue treatment with the other anti-cancer therapy in combination
During or after completion of infusion, additional appropriate medical therapy may include but is not limited to epinephrineb, IV fluids, antihistamines, NSAIDs, acetaminophen, narcotics, oxygen, vasopressors, corticosteroids.
Increase monitoring of vital signs as medically indicated until the participant recovers.
  |

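### The two-sided ±5-minute window for the end-of-infusion PK sample lets a sample be drawn before the infusion ends, which can read 12–20% low at the window's edge; a one-sided window would remove this at little cost

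*Protocol*

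**What the plan says.** The PK flowchart in Section 1.5.1 of the master protocol places a SAR444245 sample at the end of infusion (EOI) on Day 1 of Cycle 1 and of each later sampled cycle. The only other SAR444245 PK sample is on Cycle 1 Day 2. Footnote b sets the timing: "EOI samples must be taken at end of infusion (EOI) precisely ±5 minutes". Substudy 01 repeats the footnote in its own Section 1.5. Footnote a of the same table, for the anti-drug antibody sample, is one-sided: that draw must precede the start of infusion.

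The synopsis gives the infusion length: "Study sites should make every effort to target infusion timing to be as close to 30 minutes as possible", but "a window of -5 minutes and +10 minutes is permitted", so 25 to 40 minutes complies. After a Grade 2 infusion-related reaction, Table 3 of Substudy 01 says "Give the next infusion at half the infusion rate", which makes a nominal 30-minute infusion about 60 minutes.

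The only SAR444245 half-life stated is in the Introduction: "in mice and NHP to 9-13 h versus 85 min for aldesleukin in patients". No human value is given.

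Plasma concentration is a named secondary endpoint. The planned output in Section 9.4.3.7 is: "Plasma concentrations of SAR444245 will be summarized with descriptive statistics by each cohort". Section 8.4 adds that "The actual date and time (24-hour clock time) of each sample will be recorded".

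**The concern.** A symmetric window suits a quantity that changes at a similar rate on both sides of the target time. An end-of-infusion concentration does not behave that way when the infusion is short and the half-life long. Before the end, concentration climbs almost in proportion to the dose delivered, so 5 minutes of a 30-minute infusion is about one sixth of the peak. After the end, concentration falls only at the elimination or distribution rate, which is much slower.

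Both kinds of timing error pull the reading below the true EOI value, so they do not cancel. Compliant early draws would lower the summarised EOI concentration and add spread that comes from sampling time rather than from the drug. From Cycle 2 onward EOI is the only SAR444245 PK draw in a cycle, so no neighbouring sample would expose a mistimed one. What is at stake is the accuracy of one descriptive secondary summary.

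**Working it through.** The protocol states no figure for timing error, so there is none of its own to reproduce.

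**Inputs**
- Window: EOI ± 5 minutes (master Section 1.5.1; Substudy 01 Section 1.5).
- Infusion length T: 30 minutes nominal, 25 to 40 permitted (synopsis); about 60 at half rate (Substudy 01, Table 3).
- Half-life: 9–13 h, from mice and non-human primates (Introduction). Using it for humans is an assumption, varied below.

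**Model.** One compartment, constant-rate infusion, k = ln 2 / half-life.
- Early draw: C(T−5)/C(T) = (1 − exp(−k(T−5))) / (1 − exp(−kT)).
- Late draw: C(T+5)/C(T) = exp(−5k), whatever T is.

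**Worked example (T = 30 min, half-life 9 h = 540 min).** k = 0.6931/540 = 0.001284 per minute.
- Early: (1 − exp(−0.03209)) / (1 − exp(−0.03851)) = 0.03158/0.03778 = 0.836, or 16.4% low.
- Late: exp(−0.00642) = 0.9936, or 0.64% low.

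**Error at the two edges of the window, half-life 9 h to 13 h**

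| Infusion (min) | 5 min early | 5 min late |
|---|---|---|
| 25 | 19.7–19.8% low | 0.64–0.44% low |
| 30 | 16.4–16.5% low | 0.64–0.44% low |
| 40 | 12.2–12.3% low | 0.64–0.44% low |
| 60 (half rate) | 8.0–8.1% low | 0.64–0.44% low |

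**Sensitivity to the half-life (T = 30).** At 24 h: early 16.6%, late 0.24%. At 85 minutes (the aldesleukin value, used as an extreme): early 15.0%, late 4.0%. The early error hardly moves; the late error does.

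**Sensitivity to a fast distribution phase.** An assumed fast phase with weight 30–70% and half-life 30–120 minutes was added to an 11 h slow phase. At T = 30 the early error is about 14–16% and the late error about 1–7%. The narrowest gap among the permitted lengths run is at T = 40 with the strongest fast phase: 9.7% early against 6.8% late. The early error was the larger in every case run.

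**From the edge to the mean.** The figures above apply at exactly −5 or +5 minutes. The documents give no distribution of actual draw times. As an illustration, spread the draws evenly over ±5 minutes. Both errors grow almost linearly with the time offset, so each half averages about half its edge value.
- T = 30: early half about 16.4/2 = 8.2%, late half about 0.3%; overall (8.2 + 0.3)/2 ≈ 4% low.
- T = 25: (9.9 + 0.3)/2 ≈ 5% low.
- T = 40: (6.1 + 0.3)/2 ≈ 3% low.

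**With a window of 0 to +5 minutes.** The largest timing error is 0.44–0.64% under the one-compartment model at 9–13 h, or the late figures above if a fast phase exists.

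**The case against.** The strongest reply is that the protocol already limits the damage. Sample times are recorded to the clock (Section 8.4), dose dates and times go into the e-CRF (Section 6.4), and the PK analysis is reported separately from the main study report. A model-based analysis using actual times would handle an early draw correctly. This stands, and it is why the point is minor. It does not cover the descriptive summary by cohort: recorded times do not by themselves correct a mean of nominal EOI values, and a compliant early draw is not a deviation that would prompt exclusion.

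It is also fair to say that the footnote's target is the end of infusion, with ±5 minutes as tolerance, so most draws may fall close to it. A reader might infer that early draws are likely because sites cannot foresee the exact end. The documents do not support that; staff may equally wait for the pump to stop.

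A reader might also infer that site habits confound comparisons between cohorts or with the first-in-human study. Section 9.4.3.7 plans summaries by cohort and describes no PK comparison, Section 1.5.1 applies one window to all cohorts, nothing links site habit to cohort, and the first-in-human sampling window is not given.

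Nor should drug left in the line be added to the error. The current text does not say whether the end of infusion includes a flush, and the pharmacy and laboratory manuals are not shown. If it does include one, the undelivered fraction at −5 minutes would be smaller than computed here.

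Finally, a data-handling rule for mistimed samples may properly sit in the SAP. Its absence is not the point; the window itself is fixed in the protocol.

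**Conclusion.** The point holds as a minor improvement. The window permits a draw before the infusion ends, and the errors on its two sides are unequal: about 12–20% low at the early edge over the permitted infusion lengths (about 16% at 30 minutes, about 8% at half rate), against about 0.4–0.6% low at the late edge. The early figure rests on a constant-rate infusion and depends little on the half-life. The late figure assumes one-compartment kinetics at the animal half-life and becomes a few percent with a fast distribution phase.

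It would be wrong to read 16–20% as the bias of the reported mean. That range describes one sample at the very edge of the window, for the nominal and shortest infusions only. With draws spread evenly over the window, an assumption, the mean for a 30-minute infusion is about 4% low. The effect is confined to the descriptive SAR444245 concentration summaries; ORR and safety endpoints are unaffected.

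**What to change.** Reword footnote b in the master flowchart, in Substudy 01, and in any other substudy flowchart that repeats it, so that the EOI sample is drawn only after the infusion has ended, within 0 to +5 minutes. State that a sample timed before the recorded end of infusion is left out of the nominal EOI summary; it can still enter a model-based analysis at its actual time. This needs the infusion stop time to be captured, and Section 6.4 does not say whether the recorded dose time includes it.

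The cost is a footnote change, matching laboratory-manual wording, and a window of 5 minutes instead of 10. The number of samples does not change. If 5 minutes proves too tight for sites, the limit could be +10 minutes, provided human PK data show no marked fast distribution phase. At 9–13 h under the one-compartment model a draw 10 minutes late reads 1 − exp(−10k), or 0.9–1.3%, low; that extension has not been checked with a fast phase.
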